9.7 Prohibited medication and procedures

The medications listed below are prohibited during the trial from randomisation. Medications and procedures disallowed prior to randomisation are covered in the exclusion criteria (see Section 8.3). In case any prohibited treatments are used during the trial, they must be recorded as concomitant medication.

From randomisation through end of treatment (Week 26):

- PDE-4 inhibitors.
- TCS of higher potency (Europe class >3).
- Use of UVA or UVB, psoralen + UVA (PUVA), other phototherapy, or tanning beds.
- 3 or more bleach baths per week.

From randomisation through safety follow-up (Week 40):

- Investigational agents other than tralokinumab.

- Systemic corticosteroids (nasal and inhaled corticosteroids are allowed).
- Systemic treatment for AD with an immunosuppressive/immunomodulating agent (examples include: cyclosporine A, mycophenolate mofetil, azathioprine, methotrexate, Janus kinase inhibitors, interferon-gamma, dupilumab, or other biologics).

In case prohibited systemic medications are received (for any indication), IMP dosing must be suspended as described in Section 10.2.2.

The sponsor's medical expert must be notified if a subject receives any of the following prohibited medications from randomisation through safety-follow-up (Week 40):

- Allergen immunotherapy.
- Live (attenuated) vaccine.
- Immunoglobulins.
- Blood products.

The sponsor's medical expert will determine whether IMP discontinuation is required. Please note that receipt of inactive/killed vaccines (e.g. inactive influenza) is allowed, provided they are not administered within 5 days before/after any trial visit.

9.8 Treatment logistics and accountability

9.8.1 Labelling and packaging of trial products

Investigational medicinal product

The IMP will be packaged in individually numbered kits, each containing 1 syringe (tralokinumab 150 mg or placebo). Primary and secondary packaging materials (syringe and outer carton, respectively) will be individually labelled.

The labelling of IMPs will be in accordance with Annex 13, local regulations, and trial requirements. Label text will be translated into local languages, as required.

Auxiliary medicinal product

The AxMP (TCS) will be packaged in individually numbered kits that contain tubes of TCS cream with a total weight of 180–225 g. Primary and secondary packaging materials (tube and outer kit carton, respectively) will be individually labelled.

The labelling of AxMPs will be in accordance with Annex 13, local regulations, and trial requirements. Label text will be translated into local languages, as required.

9.8.2 Storage of trial products

Storage of IMP

All LEO supplied IMPs must be stored in a secure and restricted area under the conditions specified on the label and remain in the original container until dispensed.

The IMP must be stored at 2-8°C at the trial site. The temperature during storage should be monitored by a calibrated, stationary, and continuously monitoring system. Minimum requirement is a calibrated min/max thermometer. A temperature log must be kept to document the storage within the right temperature interval. Storage facilities should be checked at least every working day.

Storage of IMP may be delegated, e.g. to a hospital pharmacy, as locally applicable.

Note that in the cases listed below, site staff should not use the affected IMP and should immediately contact their CRA for further guidance:

- Temperature excursion upon receipt or during storage at the trial site.
- Damaged kit upon receipt.
- Damaged syringe.

Damaged IMP should be documented in the IRT and reported as a product complaint to Global Safety, LEO (see Section 9.10). Damaged IMP may not be used.

Further details regarding IMP storage (including handling of temperature excursions upon receipt or during storage at the trial site) and handling of damaged IMP (including kits damaged upon receipt) are provided in the trial product handling manual.

Storage of AxMP

All LEO supplied AxMP (TCS) must be stored in a secure and restricted area under the conditions specified on the label and remain in the original container until dispensed.

The TCS must be stored at the site according to the approved label for mometasone furoate. The temperature during storage must be recorded by a calibrated, stationary, and continuously monitoring system. Minimum requirement is a calibrated min/max thermometer. A temperature log must be kept to document the storage within the right temperature interval. Storage facilities should be checked at least every working day.

Storage of TCS may be delegated, e.g. to a hospital pharmacy, as locally applicable.

Note that in the cases listed below, site staff should not use the affected TCS and should immediately contact their CRA for further guidance:

- Temperature excursion upon receipt or during storage at the trial site.
- Damaged kit upon receipt.

Damaged TCS should be documented via IRT (refer to the IRT instructions for further details) and reported as a product complaint to Global Safety, LEO (see Section 9.10). Damaged TCS should not be used.

9.8.3 Drug accountability

Trial product accountability will be performed in the IRT.

IMP accountability

The investigator is fully responsible for the IMPs at the trial site and for maintaining adequate control of the IMPs and for documenting all transactions with them. Dispensing of IMPs may be delegated, e.g., to a hospital pharmacy, as locally applicable.

Individual drug accountability of the IMP administered to each subject randomised in the trial must be documented. The individual drug accountability must be available during monitoring visits and will be checked by the CRA to verify correct dispensing of the IMP. Drug accountability information will be entered in the IRT, where also inventory status of all IMP at the trial site will be maintained. For more information about IMP and AxMP accountability, please refer to the trial product handling manual.

The IMPs must be fully accounted for by the CRA with the help of site staff responsible for dispensing the IMPs. All unused IMPs supplied by the CMO on behalf of LEO will be returned to the CMO.

AxMP accountability

The number of TCS tubes returned by the subject must be documented in the eCRF by the trial staff. The subject will at each dispensing visit return used, partly used, and unused TCS tubes (including empty kit cartons) to the site. Once reconciled and accounted for, the site will return all of the above to the CMO. For further details, please see the trial product handling manual.

All returned AxMP tubes will be weighed by the CMO to determine the amount of TCS used by the subject. The detailed procedure for weighing of AxMP tubes and subsequent transfer of tube weight data to the clinical database will be documented.

Reporting in eCRF

The IMP kit numbers as well as the date and time of IMP administration will be recorded in the eCRF. In addition, the site of IMP injection should be given. For AxMP (TCS), the kit/tube number, date of dispensation and return, and number of tubes dispensed and returned will be recorded in the eCRF.

9.8.4 Treatment compliance

IMP injections will be performed by site staff that will also hand out TCS for self-administration and keep the accountability records up to date. Any non-compliance with IMP administration and dispensing and return of TCS and the reason for it must be recorded in the eCRF.

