To evaluate the efficacy of tralokinumab in combination with TCS on patient-reported outcomes compared to placebo in combination with TCS.	
 • Change from baseline to Week 16 in SF-36 score • Change from baseline to Week 26 in SF-36 score • Change from baseline to Week 16 in POEM • Change from baseline to Week 26 in POEM • Reduction from baseline to Week 16 of POEM of ≥ 4 points among subjects with baseline POEM ≥ 4 • Reduction from baseline to Week 26 of POEM of ≥ 4 points among subjects with baseline POEM ≥ 4 • Change from baseline to Week 16 in EQ-5D-5L score • Change from baseline to Week 26 in EQ-5D-5L score • Change from baseline to Week 16 in EQ-5D-5L VAS score • Change from baseline to Week 26 in EQ-5D-5L VAS score • Change from baseline to Week 16 in HADS • Change from baseline to Week 26 in HADS • HADS-anxiety and HADS-depression scores < 8 at Week 16 • HADS-anxiety and HADS-depression scores < 8 at Week 26 • Change from baseline to Week 16 in HADS-anxiety score • Change from baseline to Week 26 in HADS-anxiety score • Change from baseline to Week 16 in HADS-depression score • Change from baseline to Week 26 in HADS-depression score
To evaluate the efficacy of tralokinumab in combination with TCS on health care resource utilisation compared to placebo with TCS.	
 • Amount of TCS used from baseline to Week 16 • Amount of TCS used from baseline to Week 26 • Number of days without topical treatment use from baseline to Week 16 • Number of days without topical treatment use from baseline to Week 26

Abbreviations: AD, atopic dermatitis; ADA, anti-drug antibodies; CSA, cyclosporine A; DLQI, Dermatology Life Quality Index; EASI, Eczema Area and Severity Index; EASI75/90, at least 75/90% reduction in EASI score; EQ-5D-5L, EuroQoL 5-Dimension Health Questionnaire 5 Level; HADS, Hospital Anxiety and Depression Scale IGA, Investigator's Global Assessment; NRS, numeric rating scale; POEM, Patient-Oriented Eczema Measure; SCORAD, Scoring Atopic Dermatitis; SF-36: Short Form-36 questionnaire; TCS, topical corticosteroids.

7 Trial design

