9.2 Administration of trial products

9.2.1 Administration of IMP

The IRT will assign the required kit numbers for each subject at each dispensing visit.

Dosing visits are shown in the schedule of trial procedures (Section 4). The last administration of IMP will occur at Week 24. To ensure blinding, both treatment groups will receive the same number of injections at each visit.

The first day of dosing is considered Day 0 (visit 3, baseline). Each subject will receive 4 SC injections (each of 1 mL) to receive a loading dose of tralokinumab or placebo. At subsequent visits in the treatment period, each subject will receive 2 SC injections (each of 1 mL).

Hence, subjects in the treatment period will receive either:

- Tralokinumab 300 mg Q2W: tralokinumab 600 mg (4 mL) at baseline, then tralokinumab 300 mg (2 mL) Q2W.
- Placebo Q2W: placebo (4 mL) at baseline, then placebo (2 mL) Q2W.

IMP will be administered by a qualified, unblinded health care professional (HCP; see Section 9.3.1 for blinding details). A minimum interval of 7 days is required between 2 dosing visits. No specific treatment for an overdose is recommended. The investigator will use clinical judgement to treat any overdose if necessary. See Section 13.6.2 for further details regarding overdose.

The injections will be administered into the SC tissue of the upper arm, anterior thigh, or abdomen, separated by at least 3 cm. The injection site must be recorded in the source documents at each treatment visit and recorded in the eCRF.

Further details on IMP administration are provided in the trial product handling manual. IMP administration must be carried out according to these instructions.

After IMP administration

For the first 3 IMP dosing visits in the treatment period (i.e., Weeks 0, 2, and 4), subjects will be monitored after IMP administration for immediate drug reactions for a minimum of 30 minutes with vital signs taken at 30 minutes or until stable, whichever is later. Vital signs will be documented in the eCRF.

As with any antibody, allergic reactions to dose administration are possible. The World Allergy Organization has categorised anaphylaxis into 2 subgroups: allergic anaphylaxis

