9.2.2 Administration of AxMP

The IRT will assign the required AxMP (TCS) kit numbers for each subject at each dispensing visit. The TCS will be provided as mometasone furoate, 0.1% cream in kit sizes of 180–225 g Q2W. If needed, additional TCS kit(s) may be dispensed to the subject at a scheduled or unscheduled visit at the investigator's discretion. The amount of additional TCS dispensed must be recorded in the eCRF.

Subjects will be instructed to apply a thin film of the dispensed TCS (Europe: Class 3 [potent]) once daily to active lesions, as needed. The TCS should be discontinued when control is achieved; discontinuation should preferably be gradual and the maximum duration of treatment should not exceed 3 weeks. The safety and appropriateness of continued or repeated courses of TCS therapy will be monitored and supervised by site staff.

From randomisation (Week 0) and until last administration (at Week 24), the TCS will be dispensed and the subject must return used and unused TCS tubes at each subsequent trial visit, to assess the amount of medication used. The subjects must be instructed by the site staff on the importance of returning all used and unused TCS tubes. The site staff will return used and unused TCS tubes to the contract manufacturing organisation (CMO). The TCS tubes will be weighed at the CMO before shipment to the trial sites and again upon return.

An additional, lower potency TCS or TCI may be used at the investigator's discretion on areas of the body where use of the supplied TCS is not advisable such as areas of thin skin (face, skin fold areas, genital areas, etc.) or on areas where continued treatment is considered unsafe. The lower potency TCS and TCI will not be provided by LEO and will not be weighed, but must be registered in the eCRF as concomitant medications (see Section 9.6).

Further details on TCS dispensing are provided in the trial product handling manual. TCS administration must be carried out according to these instructions.

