9.3.1 Blinding

This is a double-blinded trial in which tralokinumab and placebo are visually distinct from each other. Neither the subject, nor the investigator or LEO staff who are involved in the treatment or clinical evaluation and monitoring of the subjects will be aware of the treatment received.

The packaging and labelling of the IMPs will contain no trace of identity. IMP is packed in identical boxes, with non-sequential kit numbers to ensure that unblinding does not occur during shipment and handling of the drug.

Since tralokinumab and placebo are visually distinct and not matched for viscosity, IMP will be handled and administered by a qualified, unblinded HCP (trained site staff) at the site who

will not be involved in the management of trial subjects and who will not perform any of the assessments.

If treatment allocation for a subject becomes known to the investigator or other trial staff involved in the management of trial subjects, LEO must be notified immediately.

Should an issue arise with the IMP (e.g., damaged kit or syringe that has been assigned to a subject prior to administration, or any other unexpected event with the kit or syringe [e.g., a malfunction during IMP administration]), the unblinded HCP at the site will contact the clinical research associate (CRA) to determine whether any specific actions are required. See Section 9.10 for details on reporting of product complaints.

The trial site will maintain a written plan detailing which staff members are blinded/unblinded and the process of IMP administration used to maintain the blind.

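### As written, Protocol 9.8.4 has the unblinded injector also hand out the as-needed topical steroid, and nothing in the plan separates the two roles

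*Protocol*

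**What the plan says.** On who injects: Protocol 9.2.1 says "IMP will be administered by a qualified, unblinded health care professional". Section 9.3.1 explains that tralokinumab and placebo look different and are not matched for viscosity, so "IMP will be handled and administered by a qualified, unblinded HCP (trained site staff) at the site". That person "will not be involved in the management of trial subjects and who will not perform any of the assessments". The subject and the investigator are blinded.

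On who hands out the topical corticosteroid (TCS): Protocol 9.8.4 says "IMP injections will be performed by site staff that will also hand out TCS for self-administration and keep the accountability records up to date".

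On how TCS is used: Protocol 9.2.2 has subjects apply a potent (Europe class 3) cream "once daily to active lesions, as needed", and stop it, preferably gradually, once control is reached. The same section says "The safety and appropriateness of continued or repeated courses of TCS therapy will be monitored and supervised by site staff" and "The subjects must be instructed by the site staff on the importance of returning all used and unused TCS tubes". Neither sentence says whether these staff are blinded. Section 9.8.3 is equally silent about who records the returned tubes.

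On controls: under 9.2.2 the IRT assigns TCS kits of a standard size (180–225 g every 2 weeks), the investigator decides on any extra kit, and the CMO weighs the tubes before shipment and after return. Section 9.3.1 requires a written site plan covering who is blinded and how IMP is given; TCS is not named in it.

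On endpoints: "Amount of TCS used from baseline to Week 16" appears in Protocol Section 6, Panel 4, with its Week 26 counterpart and days without topical treatment. All are listed under other endpoints.

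**The concern.** Both arms receive TCS, so the comparison depends on TCS being handled alike in both. Because the amount is left to need, it can respond to what a subject is told when the tubes are handed over. If the person handing them over knows the allocation, encouragement to use more or less, reminders to bring tubes back, and the tube records could differ by arm without anyone intending it.

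Such a difference could act in either direction. More TCS in the placebo arm would tend to dilute the treatment difference; more in the tralokinumab arm would tend to inflate it. Protocol Section 12 justifies the design on the ground that double-blind conditions are maintained, so a stated task that brings an unblinded person into the use of an active co-treatment deserves attention.

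**Working it through.** **Step 1. Set the sections side by side.**

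- 9.8.4: the staff who inject are the staff who hand out TCS and keep accountability records. The sentence gives both tasks to one group.
- 9.2.1 and 9.3.1: whoever injects is unblinded. 9.3.1 describes this person as trained site staff, so the term used in 9.8.4 includes them.
- 9.3.1: this person is kept out of subject management and assessments. Product hand-out is not mentioned either way.
- 9.2.2 and 9.8.3: supervision of TCS courses, instruction on tube return and tube records go to site or trial staff, blinded status unstated.
- Protocol Appendix 8, Section 4, third scenario: site staff on one video call supervise the self-injection and remind the subject to start the next TCS tubes. Blinded status is again unstated.

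Followed literally, the text puts TCS hand-out with someone who knows the allocation. No section of either document says otherwise.

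**Step 2. Ask which routes the existing controls close.**

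| Route | Control | Left open? |
|---|---|---|
| Regular supply | IRT assigns kits of standard size | Largely closed |
| Extra supply | Blinded investigator decides | Largely closed |
| Tube weights | Weighed off site by the CMO | Largely closed |
| Non-returned tubes | SAP 6.6.5 and 6.6.8: for subjects still in the study, analysed as fully used (primary) and as not used (sensitivity) | Bounded |
| Verbal advice on as-needed use | None stated | Open |
| Prompting of tube return, tube records | None stated at site | Open, within the bounds above |

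**Step 3. Ask whether the analysis would absorb a difference.** Protocol 14.3.7 lists three intercurrent events: rescue treatment, permanent discontinuation of IMP, and subject-onset of the pandemic. Use of the supplied TCS is none of these. The Mantel-Haenszel analysis in 14.3.8.1 is stratified by prior CSA use and baseline IGA only. A difference in TCS use would therefore pass into EASI75, and likewise into IGA and itch. Section 14.3.10 compares TCS amount between arms by visit, which could reveal a difference but does not correct for it.

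**Step 4. Reproduce the plan's power, then illustrate.** Inputs from Protocol 14.1, 7.2 and 14.3.16: 250 subjects at 1:1, so n = 125 per arm; two-sided 5%; EASI75 40% v 15%; pruritus response 30% v 15%. With p̄ the mean of the two rates,

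power = Φ[(|p₁ − p₂| − 1.96·SE₀)/SE₁], SE₀ = √(2p̄(1 − p̄)/n), SE₁ = √((p₁(1 − p₁) + p₂(1 − p₂))/n).

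- EASI75: p̄ = 0.275, SE₀ = 0.0565, SE₁ = 0.0542; (0.25 − 0.1107)/0.0542 = 2.57; power 99.5%. The plan says 99%.
- Pruritus: p̄ = 0.225, SE₀ = 0.0528, SE₁ = 0.0520; (0.15 − 0.1035)/0.0520 = 0.89; power 81.4%. Jointly, taking the two as independent, 0.995 × 0.814 = 81.0%. The plan says at least 80%.

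The documents give no size for any effect of TCS handling, so the shifts below are assumed.

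| Assumed shift | Result |
|---|---|
| Placebo EASI75 20% or 25% instead of 15% | Power 94% or 72% |
| Placebo pruritus response 18% or 20% instead of 15% | Power 60% or 45% |
| No drug effect, EASI75 15% in both arms, then +2, +3, +5 or +10 points on tralokinumab | Chance of a significant result favouring tralokinumab about 6%, 9%, 18% or 51%, instead of 2.5% |

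**The case against.** The best reply is that 9.8.4 is a short compliance section using a collective term, that roles are set in 9.3.1, and that dispensing detail is left to a trial product handling manual we cannot see. That may well explain the wording. It does not remove the conflict: 9.8.4 assigns the task in terms, and nothing in the protocol or SAP overrides it.

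Several stronger readings are tempting, and here the reply succeeds.

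- A reader might infer that 9.3.1 forbids the unblinded person to hand out TCS. It bars subject management and assessments and does not say whether hand-out counts as management.
- A reader might take the 9.2.2 sentence on supervising TCS courses to mean that unblinded staff do it. It says only site staff.
- A reader might suppose the unblinded person controls how much TCS a subject gets. Step 2 shows that supply and weighing are largely out of that person's hands.
- A reader might say that TCS drives EASI75. The documents give no such effect. Protocol 5.3 describes TCS efficacy as limited in moderate-to-severe disease, and inclusion criterion 5 requires inadequate response to topical medication, with systemic treatment in the past year counted as such.
- A reader might treat the power table as an estimate of loss. The 15% planning rate is already a placebo+TCS rate, so 20% or 25% supposes that differential handling raises response by a third or two-thirds in relative terms (5/15, 10/15). Nothing in the documents makes that likely or unlikely.

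**Conclusion.** The point holds as a conflict over who does what. As written, a person who knows the allocation hands out an as-needed active co-treatment and keeps the accountability records, and no text separates the roles. The open routes are verbal advice, prompting of tube return, and site records. They matter because no planned analysis adjusts EASI75, IGA or itch for TCS use. The direct effect on TCS endpoints carries less weight, since these sit outside the testing hierarchy and the SAP bounds the non-return problem.

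The size is unknown. The conclusion assumes that 9.8.4 is followed literally at sites and that the manual does not already separate the tasks. If it does, only the protocol wording needs correcting. The power and false-positive figures show sensitivity to assumed shifts and are not a forecast. The change is worth making because it replaces a stated role assignment at little cost.

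**What to change.** Reword 9.8.4 to agree with 9.3.1, for example: *The unblinded HCP handles and injects IMP only. Blinded site staff hand out TCS, instruct subjects on its use, collect returned tubes and keep TCS accountability; the unblinded HCP does not hand out or advise on TCS.* Add the same line to 9.2.2 and extend the written site blinding plan in 9.3.1 to name TCS. For visits already made, establish from site records, before the code is broken, who handled TCS, and report it in the clinical trial report.

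The cost is protocol wording and a site instruction. Blinded staff already see the subject at each site visit, so extra staff are probably not needed, though the documents do not confirm this. The small downside is a second staff contact at each of the 13 dosing visits (every 2 weeks from Week 0 to Week 24: 24/2 + 1). No dose or clinical rule changes.
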